9.3.10. Adverse events and special situations (cardiovascular events)

All AEs, Serious Adverse Events (SAE), Adverse Events of Special Interest (AESI) i.e. cardiovascular events and Special Situations (SS) occurring from each patient's enrolment to the end of the study will be collected in accordance with the process described in **Section 11**. All AEs will be assessed according to incidence, intensity, causality, outcome, action taken and seriousness.

The participating physicians and any qualified designees are responsible for detecting, documenting, and recording events that meet the definition of an AE, SAE, AESI or SS and remain responsible for following up events.

The following data will be collected:

- Non-serious AEs and Serious AEs.
- AESIs defined as cardiovascular events based on the following list:

Major Adverse Cardiovascular Event (MACE) [38]

- Acute myocardial infarction;
- Acute coronary syndrome / ischemic heart disease;
- Stroke (ischemic, haemorrhagic);
- Heart failure;
- Cardiovascular death.

Non-Major Adverse Cardiovascular Events (non-MACE)

- New onset of angina;
- Unstable angina;
- Transient ischemic attack;
- New onset atrial fibrillation;
- Unscheduled interventional cardiology procedure (stenting, CABG);
- New onset hypertension > 140/90 mm Hg (with new hypertension treatment or a posology adjustment of hypertension treatment);
- New onset or worsening of peripheral vascular disease or unscheduled intervention;

- Stent thrombosis;
- QT prolongation (calculated with the electrocardiogram Fridericia's corrected QT interval strictly higher than 450 ms (QTcF interval: QTc=QT/ $\sqrt[3]{RR}$).

The list may not be exhaustive, it could be enlarged during the course of the study and the review of the adverse events. The adverse events will be reviewed by an Independent Committee as specified in **Section 9.4**.

- Special Situations (SS) (as listed in Section 11.1.3), including pregnancies:
 - Female patients and male patients with a female partner are requested to report any pregnancy occurring during the study, along with a select set of information regarding the outcome of pregnancy and neonatal condition.
 - Pregnancy history (date confirmed);
 - Pregnancy outcome (full-term, pre-term, foetal loss/stillbirth, miscarriage, induced abortion).
 - Neonatal characteristics:
 - Respiratory distress or other complication;
 - Admission to Neonatal Intensive Care Unit and length of stay;
 - Congenital abnormalities.

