The estimates of the main endpoint will be compared among OZAWADE® users and non-users by a generalized Linear Model featuring Poisson regression. In this model we consider a post stratification model based on fixed covariates combined with a random effect attempting a correction on the expected imbalance due to the non-randomized treatment. Cumulative incidence estimate and Cox proportional Hazard regression will be used as secondary analysis.

Milestones

• Ethics submission: Q2/Q3 2024

Start of data collection: Q3/Q4 2024

• End of data collection: Q4 2030/Q1 2031

• Interim study report: yearly throughout the study

Final report of study results: Q4 2031

5. Amendments and updates

None.

6. Milestones

The planned study milestones, as per Good Pharmacovigilance Practices definitions, are summarized below.

Table 1. Study Milestones

Study Milestone	Planned date
Ethics submission	Q2/Q3 2024
Start of data collection	Q3/Q4 2024
End of data collection	Q4 2030/Q1 2031
Interim study report	Yearly throughout the study
Final report of study results	Q4 2031

7. Rationale and background

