9.1.2. Primary, secondary and exploratory endpoints

9.1.2.1. Primary endpoint

The primary endpoint will be the occurrence of at least one cardiovascular event (CVE) or one serious drug related adverse event during the five years of follow up for each participating patient.

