9.1.2.2. Secondary endpoints

The following secondary endpoints will separately investigate each type of event globally appraised by the primary endpoint:

- Time to CVE occurrence and CVE distribution in time according to classification MACE and non-MACE (See section 9.3.10)
- Time to Adverse Drug Reaction (ADR)
- Time to Serious Adverse Drug Reaction (SADR)
- Beck Depression Inventory global score at each collection time

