9.7.5. Primary Analyses

The main objective of the study is to demonstrate that OZAWADE® supplementation does not increase CV events compared with control (non-inferiority). The following analysis will be conducted:

The annual CV morbidity incidence will be estimated by the occurrence of CVE per patient per year equivalent to the proportion of patients with at least one CVE.

The CV risk is known to be higher for OSA patient with existing CV history, using or not CPAP, and well-known risk factors: diabetes, cholesterol, weight, hypertension, demographics (age, gender), lifestyle (fitness, alcohol use, smoking habits).

A generalized linear mixed model featuring Poisson regression will be based on a post stratification model based on the following fixed covariates or random effects:

- nCVE_b, prior CV history measured by the number of CV events experienced before baseline, expected as the essential predicting covariates;
- Risk factors (RF): diabetes, cholesterol, weight, hypertension, alcohol use, and smoking habits reported at baseline;
- Demographics: gender, age, country, study center
- Matched classes propensity clusters: the treatment will be non-randomized but determined by the investigator, involving an expected imbalance between groups on baseline conditions. The decision of prescribing a given medicine will be assumed on a set of baseline covariates defined in the statistical plan. As too many covariates are expected, finding sufficient exact matches is unfeasible, and the goal of subclassification is to form matched subclasses (clusters), such that in each the distribution of covariates for the treated and control groups are as similar as possible. The propensity score will be used as the scalar distance with a two-stage algorithm starting with the nearest neighbour matching and optimized by a full matching procedure [39, 40, 41].

The final model is:

CVE ~ $nCVE_b + \Sigma_i RF_i + gender + age + trt + \{country\} + Offset (log-exp) + \{center | country\} + \{cluster\}$

The notation Σ_i RF_i covers the above mentioned considered risk factors. The obvious effect of the exposure duration is measured by the offset of its logarithm. The last fixed factor is the treatment (trt) binary effect (0=control, 1=pitolisant). Country, site effect nested within country, and cluster (matched group) effects will be used as random factors (between {}).

Sensitivity Analysis

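### Section 9.3.10 lets the cardiovascular event list behind the primary endpoint grow during the study, without saying who decides, until when, or that the analysis on the current list stays primary

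*Protocol*

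**What the plan says.** Protocol section 9.1.2.1 states: "The primary endpoint will be the occurrence of at least one cardiovascular event (CVE) or one serious drug related adverse event during the five years" (the follow-up period). What counts as a CVE is found in section 9.3.10, which introduces its entries with "AESIs defined as cardiovascular events based on the following list" and gives five MACE and nine non-MACE types. The secondary endpoints (9.1.2.2) and the definition of events of special interest (11.1.4) both point back to 9.3.10.

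Directly after the list, section 9.3.10 says: "The list may not be exhaustive, it could be enlarged during the course of the study and the review of the adverse events". The next sentence says that adverse events are reviewed by an Independent Committee, with reference to section 9.4. Section 9.4 describes that review as yearly, blinded and central, and as covering adjudication into MACE and non-MACE.

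The primary analysis (9.7.5) has a non-inferiority aim and uses "A generalized linear mixed model featuring Poisson regression" with CVE as outcome and log exposure as offset. The study is open-label (9.1.1). The milestones in the abstract include "Interim study report: yearly throughout the study". The SAP is due before the first interim database lock (9.7).

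**The concern.** A confirmatory non-inferiority endpoint should be defined before outcome data accrue. Here the protocol itself says that the main component of the primary endpoint may change while they accrue. This is therefore a stated rule, not a detail left to the SAP. The clause is not tied to the SAP date and could operate after the first interim lock.

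Four things are left open: who adds an event type, up to when, whether that person is blind to exposure, and which list the primary analysis uses once an addition is made. Exposure is known at the sites, each adverse event is assessed for causality to OZAWADE (11.2.2), and the sponsor receives every serious event and every event of special interest within 24 hours (11.4.2). Someone with knowledge of exposure could therefore propose an addition. If the margin is on a ratio, adding types unrelated to treatment brings the ratio closer to 1 and adds events, which narrows the interval. Both effects make non-inferiority easier to declare.

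**Working it through.** **1. Trace the definition.** Section 9.1.2.1 uses the term CVE without defining it. Section 9.3.10 supplies the list, and 9.1.2.2 and 11.1.4 refer to it. The enlargement clause stands in 9.3.10, so it reaches the CVE part of the primary endpoint. It does not reach the serious drug-related part. Neither 9.3.10 nor 9.4 says that the committee decides on additions.

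**2. The plan's own figures.** The planned total is 502 patients (9.1.1), and section 9.9 gives 195 per group. Margin, alpha, power and control rate are not visible in the public copy, so no documented operating figure can be reproduced. All rates, margins and error levels below are assumptions.

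**3. Dilution of the risk ratio.** Assume 5-year risks on the current list of 22.5% (exposed) and 15% (unexposed), so the ratio is 1.5. Let added types carry risk *a* in both groups, independent of the current events:

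RR = [1 − 0.775(1 − a)] / [1 − 0.85(1 − a)]

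| a | Exposed | Unexposed | RR | Difference (points) |
|---|---|---|---|---|
| 0 | 22.5% | 15.0% | 1.50 | 7.5 |
| 0.05 | 26.4% | 19.3% | 1.37 | 7.1 |
| 0.10 | 30.3% | 23.5% | 1.29 | 6.8 |
| 0.15 | 34.1% | 27.8% | 1.23 | 6.4 |
| 0.20 | 38.0% | 32.0% | 1.19 | 6.0 |

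**4. Effect on a ratio-based non-inferiority test.** Let added unrelated events equal a fraction *f* of the control rate. Then RR(enlarged) = (RR + f)/(1 + f). Use an unadjusted Wald test on the log rate ratio with SE = √(1/Ec + 1/Et), where Ec and Et are the expected event counts. Take one-sided 0.025, 5 years per patient, and a true ratio on the current list equal to the margin M. The chance of declaring non-inferiority is Φ[ln(M/RR enlarged)/SE − 1.96].

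Example: 195 per group, control rate 0.05 per year, M = 1.5, f = 0.5.
- Person-years per group: 195 × 5 = 975.
- Ec = 975 × 0.075 = 73.1 and Et = 975 × 0.100 = 97.5.
- SE = 0.155; RR(enlarged) = 2.0/1.5 = 1.33.
- ln(1.5/1.333)/SE = 0.118/0.155 = 0.76, and Φ(0.76 − 1.96) = 11.5%.

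| f | RR | 195 per group | 251 per group |
|---|---|---|---|
| 0 | 1.50 | 2.5% | 2.5% |
| 0.25 | 1.40 | 6.1% | 6.8% |
| 0.5 | 1.33 | 11.5% | 13.7% |
| 1 | 1.25 | 26.8% | 33.1% |

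(251 is 502/2 and assumes equal groups.) At f = 0.5, over control rates of 0.03 to 0.10 per year, margins of 1.3 to 2.0 and both group sizes, the range is 5.8% to 50.7%.

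**5. Other scales.** On an absolute rate difference, unrelated events add equally to both groups. The difference does not move, and false non-inferiority stays at 2.5%, with more variance. On a difference in 5-year proportions, the scenario of step 4 with 195 per group and f = 0.5 gives 4.1%. The rise is modest in most scenarios but reaches 23.6% at the extreme (251 per group, 0.10 per year, margin 2.0).

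**The case against.** The strongest reply is that the clause links enlargement to the review of adverse events, and that the next sentence and section 9.4 assign that review to an independent, blinded, central committee. On that natural reading, additions would come from people who do not know exposure. This lowers the risk materially. It does not settle the matter, because the protocol gives the committee review and adjudication but not authority over the list, and it sets no cut-off.

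Other objections also stand. The margin and its scale are not shown. The Poisson model and a cited reference on the ratio of two Poisson rates suggest a ratio, but absolute risk difference is among the abbreviations. An added type might be a suspected drug effect, which would raise the ratio. The serious drug-related component is judged against OZAWADE, arises essentially in exposed patients, and works against non-inferiority. The list already has 14 entries, so an added risk of 20%, above the 15% assumed for the whole current list in the unexposed group, is an outer bound rather than an expectation.

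A reader might infer that the sponsor will extend the list after seeing results by group. The documents do not say so: the milestone only announces yearly interim reports, and no visible text says that they show the primary endpoint by group or feed into the list. A reader might also infer that any addition, even a blinded one, undermines the sample size and margin. That cannot be shown, because the event list and rate behind them are not visible.

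**Conclusion.** The point holds in limited form. Section 9.3.10 leaves the CVE component of the primary endpoint open during the study, with no stated decision-maker, cut-off, blinding condition or protected analysis on the current list. The blinded committee is a partial safeguard.

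The size of any distortion is conditional. It needs a ratio margin, additions unrelated to treatment, and the assumed rates. Under those conditions the ratio of 1.5 falls to between 1.37 and 1.19, and in the central example false non-inferiority rises from 2.5% to 11.5%. To say that the clause as such biases the study toward non-inferiority goes too far: on a rate difference there is no such dilution, and drug-related additions act in the opposite direction. The defect is that the definition can move with the data, whichever way the result then shifts. It should be corrected, and the correction is simple.

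**What to change.** Replace the enlargement clause in section 9.3.10 with a statement that the list as it stands in this protocol version defines CVE for the primary analysis. Allow later event types only by decision of the Independent Committee, blind to exposure, with date and reason logged. Report them in a separately labelled supplementary composite beside the result on the current list.

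The cost is one sentence and one supplementary table. No safety signal is lost, because section 11.4.1 already requires collection of all adverse events, serious or not and related or not. The price is that an event type recognised late as important does not enter the primary result. The supplementary composite shows it openly instead.

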9.3.11. Patient non-inclusion log

Data collected from eligible patients not enrolled in the study will be collected in such log in order to assess potential selection bias. The following data will be collected for all eligible not-enrolled patients who came to a consultation.

- Demographic data: age, gender; year of OSA diagnosis;
- Reason(s) why the patient is not participating in the study.

9.4. Data sources

This is a prospective, observational study, and patient data collected from the participating physicians will be abstracted from medical records and from administration of baseline and follow-up assessments and questionnaires (PROs and ClinROs).

The patient data will be collected from the patient medical file (original files, hospital reports, laboratory tests reports, various correspondence, etc.). Data will be entered into the electronic case report form (eCRF) using electronic data capture (EDC) via an internet browser interface.

Patients participating in the study will be identified by a unique number (pseudonymized).

[figure not shown]
Sites will be trained to the use of the eCRF. Data will be recorded by participating physicians or qualified designee.

All original source documents from which the information reported in the eCRF will be obtained must be kept up-to-date and readily available. By signing the eCRF, the participating physician will confirm the accuracy, completeness, legibility, and timeliness of the data reported to the Sponsor.

Paper PRO and ClinROs questionnaires will be used and answers will be recorded directly into the eCRF by the sites.

A yearly blinded review of the adverse events and adjudication of the events (major adverse cardiovascular events [MACE] and non-major adverse cardiovascular events [non-MACE]) will be centrally performed by an Independent Committee.

9.5. Sample size

9.6. Data management

At the study initiation, the data manager will transpose all data management steps into a Data Management Plan (DMP) to be carried out and the applicable procedures. The data management system, stakeholders, applicable procedures, data flow, organisation of data collection and coding methods will be detailed.

An electronic database specific to the study will be developed. Its characteristics will be described by an annotated CRF and a dictionary of variables and they will be validated prior to the development of the data entry tool.

The input masks will be developed and validated before they are put into production.

Procedures for checking the reliability and validity of the data entered will be defined (training, creation of input guide, double entry, reconciliation, quality control).

Data review meetings will be held around tables, listings and graphs representing the contents of the database. The strategy of taking into account the missing, outliers, etc. will be decided in agreement with Bioprojet Pharma. The set of deviations from the protocol will also be described, in particular the list of patients wrongly included. If it becomes necessary to define different patient populations for analysis, these populations will be described. All the decisions taken during this data review, prior to the analysis, will be recorded in a specific report kept in the study file.

Once this report is approved, the patient database will be locked and sent to the statistician for analysis.

9.7. Data analysis

This part summarizes the primary principles of the statistical analysis, further detailed in a SAP expected to be finalized before the first interim database lock.

9.7.1. Patient non-inclusion log

The number and percentage of eligible patients enrolled in the study will be presented as well as the reason why patients not enrolled are not participating in the study.

Moreover, age and gender will be described and compared between patients enrolled and patients not enrolled in the study, using standard statistical tests (chi-square or exact Fisher test for gender and Student t-test or Mann-Whitney Wilcoxon test for age).

9.7.2. Study populations

In this observational study, all included patients are eligible to the analysis.

9.7.3. Statistical Methodology

9.7.3.1. Missing data handling

The strategy for missing data handling may be discussed depending on the nature of missing data and the endpoint they are related to. To be in conformity with the ICHE9-R1 guidelines, these strategies for analysis may be described in a specific section of the SAP in which the concept of estimands and intercurrent events will be defined.

9.7.4. Disposition, Demographic, and Baseline Characteristics Analyses

Disposition of patients, demographics, and all baseline characteristics (as described in Section 9.3.2) will be summarized overall on the study population and by treatment group (OZAWADE® vs non-OZAWADE®).

9.7.5. Primary Analyses

The main objective of the study is to demonstrate that OZAWADE® supplementation does not increase CV events compared with control (non-inferiority). The following analysis will be conducted:

The annual CV morbidity incidence will be estimated by the occurrence of CVE per patient per year equivalent to the proportion of patients with at least one CVE.

The CV risk is known to be higher for OSA patient with existing CV history, using or not CPAP, and well-known risk factors: diabetes, cholesterol, weight, hypertension, demographics (age, gender), lifestyle (fitness, alcohol use, smoking habits).

A generalized linear mixed model featuring Poisson regression will be based on a post stratification model based on the following fixed covariates or random effects:

- nCVE_b, prior CV history measured by the number of CV events experienced before baseline, expected as the essential predicting covariates;
- Risk factors (RF): diabetes, cholesterol, weight, hypertension, alcohol use, and smoking habits reported at baseline;
- Demographics: gender, age, country, study center
- Matched classes propensity clusters: the treatment will be non-randomized but determined by the investigator, involving an expected imbalance between groups on baseline conditions. The decision of prescribing a given medicine will be assumed on a set of baseline covariates defined in the statistical plan. As too many covariates are expected, finding sufficient exact matches is unfeasible, and the goal of subclassification is to form matched subclasses (clusters), such that in each the distribution of covariates for the treated and control groups are as similar as possible. The propensity score will be used as the scalar distance with a two-stage algorithm starting with the nearest neighbour matching and optimized by a full matching procedure [39, 40, 41].

The final model is:

CVE ~ $nCVE_b + \Sigma_i RF_i + gender + age + trt + \{country\} + Offset (log-exp) + \{center | country\} + \{cluster\}$

The notation Σ_i RF_i covers the above mentioned considered risk factors. The obvious effect of the exposure duration is measured by the offset of its logarithm. The last fixed factor is the treatment (trt) binary effect (0=control, 1=pitolisant). Country, site effect nested within country, and cluster (matched group) effects will be used as random factors (between {}).

Sensitivity Analysis

For patients with prior CV history, the nCVE $_b$ covariate summarizes the CV history of the patient and was considered into the main model. For sensitivity purposes (a) the time passed between the first occurrence of

a CV event and the start of pitolisant treatment expected to estimate the CV event duration will be used as an added covariate in the model.

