9.1. Study design

9.1.1. Overall Design of the Study

This is a prospective, observational, multi-center, open-label, long term, cohort study (OZAWADE® exposed and OZAWADE® unexposed) designed to collect data on the long-term safety of OZAWADE® treatment. This study will be conducted in OSA patients with EDS whose EDS has not been satisfactorily treated by, or who have not tolerated OSA primary therapy. The study will be conducted by physicians specialized in sleep management such as sleep specialists, pulmonologists, cardiologists, otorhinolaryngologist and neurologists.

[figure not shown]
As an observational study, the assignment of the patient to a particular therapeutic strategy should be decided within the current clinical practice and the decision to prescribe OZAWADE® should necessarily precede and be independent of the decision to enrol the patient into the study. OZAWADE® should be prescribed and used based on the routine clinical practice as well as on the individual situation of each patient, according to the approved SmPC.

During the 2-year enrolment phase, 502 patients are planned to be recruited in four to five countries where OZAWADE® is on the market (*i.e.*, France, Germany, Italy and possibly Netherlands, Belgium or Spain), in approximately 8 to 15 centers per country.

Once eligible patients are enrolled, baseline data should be collected. Data collected in the CRF will correspond to data collected in routine practice in the investigating centers.

Patients will be followed-up up to five years, during which time they should be assessed by their treating participating physicians at 6, 12, 24, 36, 48 and 60 months, to follow routine care schedule.

Study visits, procedure and evaluations are summarized in the study flow (Figure 1) and schedule of assessments below (Table 2).

CPAP: Continuous Positive Airway Pressure; EDS: Excessive Daytime Sleepiness; FU: Follow-up; MAD: Mandibular Advancement Device; OSA: Obstructive Sleep Apnoea.

Figure 1: Study Flow.

PASS Protocol [P21-02/OZAWADE]

OZAWADE

Table 2. Schedule of Assessments

	Procedures ¹ /Visits	Inclusion	FU 6 Months	FU Year 1	FU Year 2	FU Year 3	FU Year 4	FU Year 5	End of study
	Visit window		6M [3-9M[12M [9-18M[24M [18-30M[36M [30-42M[48M [42-54M[60M [54-66M[
	Demography: age, gender	X	ē.						
	Profession / Socio-economic status	Х							
Patient interview	Height², weight	Х	Х	Х	X	X	X	X	Х
nten	Waist circumference	X	х	Х	X	X	X	х	Х

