9.1.3. Patient discontinuation and study termination

The patients are free to withdraw from the study at any time without prejudice to their drug prescriptions or therapeutic management. In this case, their data will be collected up to the time of withdrawal, with no additional information collected thereafter. The patients have also the right to oppose to the use of their personal data for the purpose of the study without prejudice to future medical care by the participating physician. However, in this case and in the case of withdrawal, any adverse events (AE) will still be

collected/reported and followed-up until resolved or stabilised or until the patient died or is lost to follow-up.

Missing evaluations at one or several time points is not a criterion for patient withdrawal.

A patient may be withdrawn from the study prior to completion in case of patient consent withdrawal and physician's or Sponsor's decision and/or safety reason. If the patient withdraws or is withdrawn, the reason will be collected in the eCRF.

All patients discontinuing OZAWADE® will be maintained in the study until completion of the follow-up period.

The participating physicians may interrupt their participation to the study at any time and will immediately inform Bioprojet Pharma.

Bioprojet Pharma reserves the right, at any time, to discontinue enrolment of additional patients into the study, at any site; or to discontinue the study, for medical or administrative reasons and will inform all study stakeholders.

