9.7.6. Secondary Analyses

The following secondary analyses will be conducted:

- The cumulative incidence, CI(t), of events at time t will be estimated using the incidence density at that time, ID(t), in the equation CI(t)=1-exp^{-ID(t)*t}. Each point of the graph provides the cumulative incidence after t years of follow-up in the study, expressed as a percentage.
- A Cox proportional model will be adapted to multiple unordered events: the Time-varying covariates will be used, this technique is acceptable for unordered events (events can occur in any order). The cluster term will be used to compute a robust variance for the model. The term cluster(id) where each value of id is unique produces an approximate jackknife estimate of the variance. If the id variable is not unique, but identifies clusters of correlated observations, then the variance estimate is based on a grouped jackknife. The model will be used according to the following notes:
 - 1- Time-varying covariates will need to replace one record by n records, such as each new record describes a time-slice where covariates are fixed (inter-visit periods). Each such record remains independent while the endpoint occurrence only happens once (single event). If multiple events occur during the follow up, the time-slices are not independent for the same patient, thus the covariance between each row must be accounted by using sandwich robust variance cluster option. This technique is acceptable for unordered events (events can occur in any order). The cluster term is used to compute a robust variance for the model (approximate jack knife estimate).
 - 2- Time-varying effect means that PH is not constant in time. The major assumption of CPH is the lack of interaction of the covariates with time. This will be tested in the Schoenfeld test, on each covariate. If one or more covariate provides evidence of interaction with time, strata(variable) where variable is categorical, allows to model baseline F(t) calculated separately for each category of the variable.
 - 3- The model will be built both in stratifying with and without regrouped center and country.

9.7.6.1. *Effectiveness analysis*

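### Section 9.7.5 equates a yearly event rate with a proportion, and its Poisson model is not aligned with the yes/no five-year primary endpoint

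*Protocol*

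**What the plan says.** - **Endpoint (protocol 9.1.2.1).** It is binary: "the occurrence of at least one cardiovascular event (CVE) or one serious drug related adverse event during the five years of follow up".
- **Measure (9.7.5).** Annual CV morbidity is "estimated by the occurrence of CVE per patient per year equivalent to the proportion of patients with at least one CVE".
- **Model (9.7.5).** "A generalized linear mixed model featuring Poisson regression will be based on a post stratification model". The equation is presented as final. Its outcome is labelled CVE, its random effects are country, center within country and matched cluster, and its offset is the log of exposure: "The obvious effect of the exposure duration is measured by the offset of its logarithm".
- **Follow-up.** "Patients will be followed-up up to five years" (9.1.1). "All patients discontinuing OZAWADE® will be maintained in the study until completion of the follow-up period" (9.1.3). No section ends a patient's person-time at a first event.
- **Rate and risk (9.7.6).** "The cumulative incidence, CI(t), of events at time t will be estimated using the incidence density at that time", with CI(t) = 1 − exp(−ID(t)·t). For the secondary Cox model, the same section says that time-slices of a patient with several events are not independent and require a robust variance.

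**The concern.** A Poisson model with a time offset estimates a ratio of events per unit of time. It does so correctly in two cases: a first-event indicator with time stopped at that event, or an event count with all follow-up time. Section 9.7.5 commits to neither, and the one sentence that links the outcome to the rate is wrong.

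The primary objective is to show non-inferiority on cardiovascular safety, so what matters is whether an open reading makes a harmful drug look acceptable. One reading moves the ratio towards 1. Another leaves the ratio alone but can understate its standard error. An analyst could follow 9.7.5 literally and arrive at either.

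**Working it through.** **No plan figure to reproduce.** The visible text of section 9.5 and Appendix 1 gives no event rate, margin, alpha or power. The control rates λ, the margins, the constant hazard and the one-sided 2.5% level below are assumptions. The five-year horizon comes from 9.1.2.1.

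**1. The equivalence clause against the 9.7.6 formula.** Put t = 5 into CI = 1 − exp(−λt):
- λ = 0.02: 9.5%, or 1.90% per year
- λ = 0.05: 22.1%, or 4.42% per year
- λ = 0.10: 39.3%, or 7.87% per year
- λ = 0.20: 63.2%, or 12.6% per year

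Rate and annualised proportion nearly agree at low rates and separate as the rate rises.

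**2. Indicator, with time running to five years.** Every patient contributes five years, so the fitted ratio is [1 − exp(−5λ·RR)] / [1 − exp(−5λ)].

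| λ | Control risk | Risk, RR 1.5 | Ratio | Risk, RR 2.0 | Ratio |
|---|---|---|---|---|---|
| 0.02 | 9.52% | 13.93% | 1.46 | 18.13% | 1.90 |
| 0.05 | 22.12% | 31.27% | 1.41 | 39.35% | 1.78 |
| 0.10 | 39.35% | 52.76% | 1.34 | 63.21% | 1.61 |

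At λ = 0.01 the ratios are 1.48 and 1.95. A true ratio of 1 stays at 1. With 5% dropout per year the result hardly moves (1.35 instead of 1.34 at λ = 0.10, RR 1.5).

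**3. The two aligned choices.** In simulations of 1,000,000 patients per scenario (λ = 0.02, 0.10 and 0.20), stopping time at the first event gave 1.49 to 1.51 for a true 1.5 and 1.99 to 2.02 for a true 2.0. A count over full follow-up also recovered the true ratio.

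**4. Net effect on the test under reading 2.** Take 251 per group (502/2), no covariates or clustering, and a true rate ratio equal to the margin. Let k0 and k1 be the numbers of patients with an event. The model-based variance of the log ratio is 1/k0 + 1/k1. This is too large for 0/1 data, where the variance is about 1/k0 + 1/k1 − 2/n. Summing over the binomial distributions of k0 and k1 gives the chance of wrongly declaring non-inferiority:
- margin 1.5: 2.4%, 3.0% and 6.7% at λ = 0.02, 0.05 and 0.10
- margin 2.0: 3.1%, 7.2% and 37%

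With the 195 per group named in section 9.9, the values at λ = 0.10 are 5.1% and 27%. Stopping time at the first event keeps the error at about 2.4% to 2.8%.

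If the smaller, robust variance is used but time still runs on, the error at 251 per group, margin 1.5 and λ = 0.10 rises from 6.7% to 21%.

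**5. Count reading.** Let θ be the between-patient frailty variance, assumed to be 1, and let μ = 5λ and 5λ·RR be the expected counts. The Poisson variance of the log ratio is (1/n)(1/μ0 + 1/μ1); the true variance adds 2θ/n. With RR = margin = 1.5:
- λ = 0.05: n × variance is 4 + 2.667 = 6.667 against 8.667. The SE is too small by a factor √1.30 = 1.14, and the error is Φ(−1.96/1.14) ≈ 4.3%.
- λ = 0.10: 2 + 1.333 = 3.333 against 5.333. The factor is √1.60 = 1.265, and the error is about 6.1%.

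**The case against.** A reader might infer that the primary model certainly divides first-event indicators by the whole of follow-up and therefore shrinks the rate ratio. The documents do not say so. Section 9.7.5 speaks only of exposure duration, and section 9.1.3 keeps patients under observation without defining the offset. The wrong equivalence clause does not by itself bias any estimate. Shrinkage arises under one reading of three.

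A reader might also infer that under that reading the model estimates nothing useful. It estimates approximately a five-year risk ratio, which is a valid measure and fits the yes/no endpoint. It misleads only against a rate-ratio margin, and no margin is visible. The Poisson standard errors are then too wide, which works against non-inferiority.

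Nor should a one-year risk of 4.9% be set against a five-year proportion of 22.1% at λ = 0.05 to claim a 4.5-fold error. Most of that gap is the change of horizon; on an annual basis, 0.05 and 4.9% differ by about 2%.

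Finally, section 9.7.6 already plans a cumulative-incidence curve and a Cox model for multiple events with robust variance, and section 9.7 defers detail to a SAP. All of this stands as a limit on the point. It does not remove it: the protocol itself writes out a final equation and links it to the endpoint by an incorrect statement, which the SAP would inherit.

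**Conclusion.** The point holds in conditional form. The equivalence clause is wrong and conflicts with 9.7.6, and the final model is not aligned with the endpoint in 9.1.2.1. The consequence depends on the reading:

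- **Indicator, time running on.** The ratio lies closer to 1 than the rate ratio. Under a rate-ratio margin the net effect on the error rate is negligible at 1–2% per year. It becomes material at about 10% per year, or at 5% per year with a margin of 2.0.
- **Count.** The ratio is unbiased, but there is no patient-level term or robust variance, so the error rate may rise modestly. The size rests on the assumed frailty variance.
- **First event, time stopped there.** No problem.

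The CVE list in 9.3.10 is broad, including new hypertension with treatment change and QTcF above 450 ms, so a higher rate is plausible, but it remains an assumption. The text should be corrected before the analysis is fixed. It does not show that the primary result will be biased.

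**What to change.** In section 9.7.5:
1. Delete the clause that equates the yearly rate with the proportion.
2. Define the primary outcome as the first adjudicated endpoint event (0/1). Name its components, since 9.1.2.1 also counts serious drug-related adverse events while the model names only CVE.
3. Define the offset as the log of time from inclusion to first event, death, withdrawal or end of follow-up.
4. Use robust standard errors. Adopt this together with item 3, because a robust variance without stopping the clock increases the error (step 4 of the working).
5. State that the non-inferiority margin is a rate ratio, the scale on which the model estimates.
6. Report the five-year risk from the cumulative-incidence analysis already planned in 9.7.6. Keep recurrent events secondary, with a patient-level term or robust variance.

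The cost is a few sentences in 9.7.5, carried into the SAP. Time to CVE is already a secondary endpoint, so event timing is needed anyway. No new visits or patients are required. If the margin was set on another scale, the sample-size calculation should be checked against it.
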